10.2.2.1 Duration of HAE Attacks

The duration of each HAE attack in days will be derived by:

$$\text{HAE attack's end date} - \text{HAE attack's start date} + 1.$$

The following will be summarized descriptively:

- The duration of all HAE attacks.
- The per-subject average duration of HAE attacks.

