10.3 Statistical Analyses and Methods

Analysis datasets will be created according to Clinical Data Interchange Standards Consortium (CDISC) standards, and data will be displayed according to reporting standards described in the SAP.

Continuous variables will be described by the number of observations, mean values with their 95% confidence intervals (CIs), SD, 25th percentile, median (50th percentile), 75% percentile, and range (minimum to maximum). The geometric coefficient of variation will be expressed as a percentage for PK and PD data and will be calculated as $100 \times \sqrt{\exp(\text{SD}_{\log}^2) - 1}$. The geometric mean and its 90% CI will be calculated for PK and PD data. The geometric mean and its 90% CI will be calculated by log-transforming the data, calculating the mean and the lower and upper limits of the 90% CI of the log-transformed data, and subsequently back transforming the mean and the lower and upper limits. Categorical variables will be summarized using frequency counts and percentages.

No hypothesis testing is planned for this study.

As it is expected that the coronavirus disease 2019 (COVID-19) pandemic is still ongoing during the conduct of the study, it will be assessed for subjects who are affected by COVID-19 during their participation in the study if they will be excluded from some analyses.

Reasons for an exclusion will be documented. The impact of COVID-19 will be summarized. Listings of COVID-19-associated AEs will be provided for any AEs. Treatment-emergent adverse events (TEAEs) occurring or not occurring within 7 days of a COVID-19 vaccination will be summarized. Concomitant medications used to treat COVID-19-associated AEs will be flagged. COVID-19 vaccinations will be assessed. COVID-19-related protocol deviations will be summarized, and all COVID-19-related protocol deviations will appear in the listing of protocol deviations and will be flagged. All protocol deviations will be reviewed during the Data Review Meeting.

A complete description of the statistical analyses and methods will be available in an SAP, which will be finalized before the database is locked.

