6.6 Pharmacodynamic Analysis Set

The PD Analysis Set comprises all subjects in the Safety Analysis Set for whom at least 1 PD measurement was obtained.

7 General Considerations

Datasets will be created according to Clinical Data Interchange Standards Consortium (CDISC) standards. Study data will be provided in Study Data Tabulation Model (SDTM) format. Analysis data will be provided in Analysis Data Model (ADaM) format.

SAS version 9.4 or higher will be used to perform all data analyses.

Summaries of continuous variables will be in terms of the number of observations, mean, standard deviation (SD), median, first quartile (Q1), third quartile (Q3), 95% confidence interval (CI), minimum, and maximum. Other descriptive statistics (eg, standard error, coefficient of variation) may be reported when appropriate. Categorical variables will be summarized using frequency counts and percentages. Analyses that use other descriptive statistics will have the specific descriptive statistics identified with the analysis in the applicable SAP section.

All listings will contain the subject identifier (ID). Listings will generally be sorted first by site and within site by subject ID.

The main listing of TEAEs (see [Section 11.4](#)) and the listing of individual HAE attacks (see [Section 10.2.1](#)) will include the most recent CSL312 dose (level, device [NSD or AI] and date).

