10.2.1.1 Time-normalized number of HAE attacks

The time-normalized number (per month) of HAE attacks is calculated per subject as:

$$\frac{\text{the number of HAE attacks}}{\text{length of subject treatment in days}} * 30.4375$$

where the length of subject treatment is calculated as the duration of the Treatment/Efficacy evaluation period described in [Section 8.4](#).

To transform the length of subject treatment which is calculated in days in years the number of days is divided by 365.25. Thus, time-normalized number of HAE attacks per year is calculated per subject as:

$$\frac{\text{the number of HAE attacks}}{\text{length of subject treatment in days}} * 365.25$$

The time-normalized number of HAE attacks will also be calculated for the Run-in Period. For non-CSL312-naïve subjects, the Run-in Period of their previous CSL312 study will be used.

The time-normalized number of HAE attacks per month and per year will be summarized descriptively including median (primary measure of interest) and mean (secondary measure of interest) with corresponding 95% CIs. The CIs for the mean will be based on the t-distribution while distribution-free CIs will be used for the median.

Besides the time-normalized number of HAE attacks, the total number of HAE attacks (ie, not time-normalized) will also be summarized.

10.2.1.2 The Reduction in the Attack Rate during the Treatment Period compared to the Run-in Period

The secondary efficacy endpoint of the percentage reduction in the time-normalized number of HAE attacks is calculated within a subject as:

$$100 * \left(1 - \frac{\text{time normalized number of HAE attacks per month during treatment}}{\text{time-normalized number of HAE attacks per month during Run-in}} \right)$$

and will be summarized descriptively. For non-CSL312-naïve subjects, the Run-in Period of their previous CSL312 study will be used.

The number and percentage of responders and non-responders will be presented combined with corresponding 95% CI. A subject is classified as a responder if the percentage reduction in HAE attacks under treatment compared to the Run-in Period is $\geq 50\%$. In addition, the number and percentage of subjects with percentage reductions of $\geq 70\%$ and $\geq 90\%$ will be presented with corresponding 95% CIs.

Furthermore, the number and percentage of subjects with a percentage reduction of 100%, ie, who are attack-free, will be presented and summarized with corresponding 95% CI.

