10.2.1.3 The Time-normalized number of HAE Attacks requiring on-demand treatment

An HAE attack requiring on-demand treatment is identified using the HAE Attack page of the eCRF, where whether on-demand treatment was required is a field to be filled out.

The time-normalized number of HAE attacks per month requiring on-demand treatment is calculated as:

$$\frac{\text{number of HAE attacks requiring on demand treatment during treatment period}}{\text{length of subject treatment in days}} \\ * 30.4375$$

and will be summarized descriptively. To report in years, the number of days will be multiplied by 365.25 instead of 30.4375.

This summary table will also include a categorical breakdown of the used on-demand medication by ATC and PT, including number and percentage of subjects who took a specific medication at least once and the total number of times a specific on-demand medication was used across all subjects. For each on-demand medication by ATC and PT, the number of uses of the on-demand medication per HAE attack will be summarized descriptively.

Both the categorical overview and the time-normalized number of HAE attacks will also be provided for moderate/severe HAE attacks.

The time-normalized number of HAE attacks will also be calculated for the Run-in period. For non-naïve subjects, the Run-in period from the previous study will be used.

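### By default, the attack-level summaries (duration of all HAE attacks, on-demand uses per attack) carry a 95% CI with no stated method; the standard interval on pooled attacks is too narrow if attacks within a subject are positively correlated

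*SAP*

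**What the plan says.** SAP 10.2.2.1 lists two descriptive summaries of attack duration: "The duration of all HAE attacks" and "The per-subject average duration of HAE attacks". Because the second is separate, the first must pool attacks across subjects.

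SAP 10.2.1.3 says that, for each on-demand medication, "the number of uses of the on-demand medication per HAE attack will be summarized descriptively". The unit is again the attack, and no per-subject version is named.

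Neither section mentions a confidence interval. It comes from SAP Section 7 (General Considerations), whose default list for continuous variables includes "first quartile (Q1), third quartile (Q3), 95% confidence interval (CI), minimum, and maximum". Section 7 also sets the rule for departing from that list: "Analyses that use other descriptive statistics will have the specific descriptive statistics identified with the analysis in the applicable SAP section". Neither section identifies any other statistics. Protocol 10.3 has a similar default, the mean with its 95% CI.

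The one CI method given for a mean or median of attack data is in SAP 10.2.1.1: "The CIs for the mean will be based on the t-distribution while distribution-free CIs will be used for the median". It is written for attack rates, where each subject contributes one value. Neither document gives a clustered variance, a mixed model, GEE or a bootstrap for the attack-level rows, or says that their CI is left out.

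**The concern.** A t interval for a mean takes the number of observations as the number of independent pieces of information. In these rows an observation is an attack, and one subject can supply several. The SAP expects this, since Section 10.3.1 analyses times to second and third attacks. Treatment lasts at least 12 months, with visits scheduled to Month 42.

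Attacks in one subject may well resemble each other in duration. Subjects also use an on-demand medication of their choice (Protocol 5.2.1.1), so uses per attack may depend on the subject. If so, the effective sample size is smaller than the attack count, and the interval claims more precision than the subjects support. The shortfall grows with attacks per subject and with how unevenly attacks are spread.

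At stake is the accuracy of a printed 95% interval, not a test or a decision.

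**Working it through.** **The plan's own figure.** The documents give no figure for these intervals beyond the nominal 95%. The plan's one numeric precision statement (SAP 4.4) concerns AEs. It reproduces, 1 − 0.97^100 = 0.952, but has no bearing here.

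**Inputs from the documents**
- About 150 subjects (SAP 4.4).
- Attack rate 0.05 per month, the phase 2 200 mg mean (Protocol 1.2.3.2).
- Treatment of at least 12 months, variable by subject (Protocol 3.4).

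**Assumed**
- Follow-up T uniform on 12 to 36 months.
- Attack counts Poisson, with subject rates gamma-distributed, shape k from 0.4 (very uneven) to 2.5.
- ICC 0.05, 0.10 or 0.20.

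**Step 1: attacks per subject.** Mean T is 24 months, so the mean count is 0.05 × 24 = 1.2, or about 150 × 1.2 = 180 attacks in all.

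**Step 2: design effect.** With m attacks in a subject, the variance of the pooled mean is inflated by

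D = 1 + (Σm²/Σm − 1) × ICC.

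Under the gamma-Poisson model the bracket is approximately rate × (E[T²]/E[T]) × (1 + 1/k).
- E[T²] = 24² + 24²/12 = 576 + 48 = 624, so E[T²]/E[T] = 624/24 = 26 months.
- Rate × 26 = 0.05 × 26 = 1.3.
- k = 2.5: 1.3 × 1.4 = 1.82, so D = 1 + 1.82 × ICC.
- k = 0.4: 1.3 × 3.5 = 4.55, so D = 1 + 4.55 × ICC.

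**Step 3: coverage of the unadjusted interval.** Approximately 2Φ(1.96/√D) − 1. The last column is a simulation of the same set-up with a continuous outcome.

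| ICC | D (k = 2.5 to 0.4) | √D | Coverage, formula | Coverage, simulated |
|---|---|---|---|---|
| 0 | 1 | 1 | 95% | – |
| 0.05 | 1.09 to 1.23 | 1.04 to 1.11 | 93.9% to 92.3% | about 93-94% |
| 0.10 | 1.18 to 1.46 | 1.09 to 1.21 | 92.9% to 89.6% | about 91-93% |
| 0.20 | 1.36 to 1.91 | 1.17 to 1.38 | 90.7% to 84.4% | about 86-90% |

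At the most uneven shape the formula falls up to about 1.6 points below the simulated lower end; otherwise the two agree. √D is the factor by which the interval should be wider. In the simulation a subject-clustered interval covers about 94-95%.

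**Step 4: higher attack rates.** The same formula at ICC 0.05 gives:
- 0.15 per month (assumed): D = 1 + 0.05 × (3.9 × 1.4 to 3.9 × 3.5) = 1.27 to 1.68, coverage about 92% to 87%.
- 0.35 per month: D = 1 + 0.05 × (9.1 × 1.4 to 9.1 × 3.5) = 1.64 to 2.59, coverage about 87% to 78%.

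The 0.35 value is the phase 2 600 mg mean, not the dose in this study, so it serves only as an outer bound.

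**Not covered.** The simulation treats one continuous outcome over all attacks. On-demand uses are small counts, summarised separately for each medication, and no coverage figure was derived for that structure.

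**The case against.** The strongest reply is that neither section plans an attack-level CI in words. Both ask only for a descriptive summary, and nothing in the SAP says that attacks are treated as independent. Where the SAP explicitly attaches intervals to attack endpoints (rates, responders, attack-free subjects), they are subject-level. For duration the subject-level summary is the very next bullet. At the 200 mg rate and a small ICC the loss is one or two points. No hypothesis testing is planned (Protocol 10.3), and efficacy is exploratory (SAP 10.4). Duration sits under supplementary analyses, and uses per attack is a breakdown inside another endpoint's table; neither is a listed endpoint.

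Most of this stands and limits the point. It does not remove it. Section 7 supplies the CI unless a section says otherwise. Other sections do name their own statistics without one, such as maximum attack-free time (SAP 10.3.1) and PK parameters (SAP 12.2), so an exemption was available. The per-subject average estimates a different quantity, weighting subjects rather than attacks, so it does not correct the pooled interval beside it. It also has no counterpart for on-demand uses.

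A reader might infer three stronger things that the documents do not support:
- **That the SAP specifies an interval assuming independence.** It specifies a default CI and no method. Independence follows only if the standard formula is applied.
- **That coverage collapses to between 53% and 79%.** Such figures need the 600 mg arm's rate. For example, 53% takes 0.35 per month, shape 0.4 and ICC 0.20: D = 1 + 0.20 × 31.85 = 7.37. SAP 4.2 states that no dosing modifications occurred prior to Amendment 1, and none are permitted under it.
- **That a few frequent attackers supply most of the attacks.** This is plausible but not stated; the gamma shapes are assumptions.

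**Conclusion.** The point holds as a minor error in planned descriptive output. Following the SAP as written, with the usual t interval, gives attack-level CIs that are too narrow for any positive within-subject correlation and correct at zero correlation. The direction is firm; the size is not, because the documents give neither an ICC nor the spread of attack counts.

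At the study dose's phase 2 rate, and for the ICCs tried, nominal 95% coverage falls to somewhere between the mid-80s and 94%. It would be lower if attacks prove more frequent than 0.05 per month. These figures apply to a continuous outcome such as duration. For on-demand uses per attack only the direction carries over.

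The primary safety endpoint, the listed secondary efficacy endpoints and the per-subject duration average are unaffected.

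**What to change.** Amend SAP 10.2.2.1 and 10.2.1.3 in one of two ways.

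1. State that attack-level rows are presented without a CI. Keep the CI on the per-subject average duration, and add a per-subject average of on-demand uses per attack with its own CI.
2. Keep the CI on attack-level rows, computed with subjects as clusters: a subject-clustered variance (for example, an intercept-only GEE with robust standard errors) or a bootstrap that resamples subjects.

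The first is simpler. It is also safer for the per-medication rows, where few subjects may contribute and a clustered variance is less reliable.

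The cost is one or two sentences of SAP text and a little programming. No new data are needed. Under the second option, the intervals become somewhat wider: by 4% to 38% over the ICCs and shapes tabulated at 0.05 attacks per month (√D of 1.04 to 1.38).

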10.2.2.2 Number and Proportion of Attack-free Days

The number of attack-free days will be calculated per subject. For each date included in the Treatment/Efficacy evaluation period it will be checked whether the subject has an HAE attack with:

$$\text{HAE Attack Start Date} \leq \text{Date} \leq \text{HAE Attack End Date}$$

If no such attack exists, that day will be considered attack-free.

The proportion of attack-free days will be calculated as a percentage:

$$100 \frac{\text{Number of attack-free days}}{\text{Duration of Efficacy evaluation period (days)}}$$

The number of attack-free days per month will then be calculated as 30.4375 days times the proportion of attack-free days.

The number and proportion of attack-free days as well as the duration of the Efficacy evaluation period and the number of attack-free days per month will be summarized descriptively.

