8.2.2 Durations and Time to Event Data

Durations (eg, the duration of an AE) are calculated in days as:

- event end date – event start date + 1, if end time or start time not available.
- event end date / time – event start date / time, if both end time and start time available.

Thus, there will be no duration of 0. If an AE has missing or partially missing start or end date, no duration will be calculated.

For elapsed time (eg, the time to event), use:

- (event date – reference date) or
- event date / time – reference date / time, if time available.

Thus, an event which happens on the same date as the reference date will have an elapsed time of 0 if event time or reference time are not available.

To transform durations or elapsed times, which are calculated in days into weeks, divide the number of days by 7; to report in months, divide the number of days by 30.4375; to report in years, divide the number of days by 365.25. These algorithms return decimal numbers and ignore the actual numbers of days in the months or years (the calendar days) between start date and stop date. The "year" used in these algorithms is 365.25 days long, and the "month" is one twelfth of that year.

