8.4 Study Periods Relative to Treatment

AEs, HAE attacks, laboratory data, vital signs and other measurements will be assigned to the study time periods defined below.

Table 3 Definitions of Study Periods Relative to Treatment

Period	Start Date	End Date
Screening Period	Date of Informed Consent	Run-in Period Start Date
Run-in Period	Run-in Period Start Date	Day 1 Visit date of the Treatment Period or Date of Run-in Non-completion [whichever is first]
Treatment/Efficacy evaluation period	Date of Day 1 Visit of Treatment Period	Date of EOT Visit or EOS date [whichever is first]
Treatment/Efficacy before transition to AI evaluation period	Date of Day 1 Visit of Treatment Period	Date of first dose with AI – 1 Day (see Section 8.2.1)
Treatment/Efficacy after transition to AI evaluation period	Date of first dose with AI (see Section 8.2.1)	Date of EOT Visit or EOS date [whichever is first]
Follow-up	Date of EOT Visit	Date of Final/ Follow-up Visit
Safety evaluation period	Date and start time of First CSL312 Administration as entered in the eDiary	Date of Final/ Follow-up Visit
Safety Evaluation before transition to AI evaluation period	Date and start time of First CSL312 Administration as entered in the eDiary	Date of first dose with AI – 1 Day (see Section 8.2.1)
Safety Evaluation after transition to AI evaluation period	Date of first dose with AI (see Section 8.2.1)	Date of Final/ Follow-up Visit

The EOS date is the date entered in the Conclusion of Subject Participation eCRF page and should generally be identical to the date of the Follow-up Visit.

The handling of any unplanned dose changes or device changes will be discussed in the PARM. The safety evaluation period consists of the Treatment/Efficacy evaluation period plus the Follow-up Period.

Screening and Run-in periods will not be performed for roll-over subjects, instead relevant endpoint data (such as HAE attacks during the Run-in period) will be used from the CSL312_2001 and CSL312_3001 studies.

The duration of the Efficacy evaluation and the Safety evaluation period in days will be calculated as:

End Date – Start Date + 1 Day.

Screening, Run-in and Follow-up periods in days will be calculated as:

End Date – Start Date.

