$\min \Sigma \text{ items}$ is the sum of the minimum score 1 which is added up as many times as there are non-missing item scores within a dimension or all items, respectively,

$\max \Sigma \text{ items}$ is the sum of the maximum score 5 which is added up as many times as there are non-missing item scores within a dimension or all items, respectively.

For the following example for the dimension “Functioning”:

Item 1: Occasionally (3)

Item 2: Rarely (2)

Item 3: Often (4)

Item 4: Very Often (5)

the AE-QoL score would be calculated by

$$\Sigma \text{ items: } (3+2+4+5) = 14$$

$$\text{min } \Sigma \text{ items: } (1+1+1+1) = 4$$

$$\text{max } \Sigma \text{ items: } (5+5+5+5) = 20$$

resulting in $[(14 - 4) / (20 - 4)] \times 100 = 62.5\%$.

The four AE-QoL scores for the four different dimensions should not be calculated if more than one item is missing in that dimension. The AE-QoL total score should not be calculated if more than 4 items are missing.

The scores are range between 0 and 100 %. The higher the percentage the stronger the impairment the subject has.

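### Attack-free days per month is computed from a percentage without dividing by 100, so the rule as written gives values 100 times too large

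*SAP*

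**What the plan says.** SAP Section 10.2.2.2 counts, for each subject, the dates in the Treatment/Efficacy evaluation period on which no HAE attack was in progress. It then gives two linked derivations.

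- **Proportion.** "The proportion of attack-free days will be calculated as a percentage". The displayed formula is 100 times the number of attack-free days, divided by the duration of the efficacy evaluation period in days.
- **Monthly figure.** "The number of attack-free days per month will then be calculated as 30.4375 days times the proportion of attack-free days".

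The count, the proportion and the period duration are to be reported, and the section adds that "the number of attack-free days per month will be summarized descriptively".

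The inputs are fixed elsewhere in the SAP. Section 8.2.2 sets the length of a month: "to report in months, divide the number of days by 30.4375". Section 8.4 sets the duration of the period as end date minus start date plus 1 day.

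The protocol does not define this analysis. The SAP modification history lists it as new in version 2.0, so Section 10.2.2.2 is its only specification. Table 5 of the SAP repeats it by CSL312-naïve status, by treatment-naïve status and for Japanese subjects.

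**The concern.** The same named quantity appears in both derivations, and the second follows directly from the first. Once the proportion carries a factor of 100, multiplying it by the length of a month carries that factor into the monthly figure. Nothing in the section removes it.

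A count of attack-free days per month cannot exceed the length of a month, 30.4375 days under Section 8.2.2. The rule as written passes that limit for any subject with more than 1% of days attack-free, because 30.4375 × 1 is already 30.4375.

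What is at stake is the monthly figure in one descriptive analysis, overall and in the Table 5 subgroups. Under the default summaries of SAP Section 7, the mean, SD, quartiles and 95% confidence limits would all be on the wrong scale.

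**Working it through.** **Inputs**

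- F = number of attack-free days (SAP 10.2.2.2)
- D = duration of the efficacy evaluation period in days (SAP 8.4)
- Month = 365.25 / 12 = 30.4375 days (SAP 8.2.2)

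The documents give no worked example or numerical result for this analysis, so there is no stated figure to reproduce. The F and D values below are illustrative assumptions. D = 361 and D = 721 match the Month 12 and Month 24 visit days.

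**Formulas**

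1. Proportion as defined: P = 100 × F / D
2. Monthly figure as written: 30.4375 × P = 30.4375 × 100 × F / D
3. Monthly figure with the scale removed: 30.4375 × P / 100 = 30.4375 × F / D
4. Independent check, using the month conversion directly: F / (D / 30.4375)

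**Results**

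| D | F | P | As written (2) | Scale removed (3) | Check (4) |
|---|---|---|---|---|---|
| 361 | 361 | 100.00 | 3,043.75 | 30.4375 | 30.4375 |
| 361 | 350 | 96.95 | 2,951.00 | 29.51 | 29.51 |
| 361 | 180 | 49.86 | 1,517.66 | 15.18 | 15.18 |
| 721 | 700 | 97.09 | 2,955.10 | 29.55 | 29.55 |

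Formulas (3) and (4) agree in every row. The ratio of (2) to (3) is exactly 100 whenever F is above 0; at F = 0 both are 0. The factor therefore does not depend on the values chosen. At P = 98 the two results are 30.4375 × 98 = 2,982.9 and 30.4375 × 0.98 = 29.83.

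**Which scale does the SAP use for its percentages?** Three places outside this section bear on the reading.

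- Section 10.6 defines compliance as 100 times a ratio and bands it at 80% and 100%.
- Section 10.3.2 scores the AE-QoL as 100 times a ratio, with a worked example giving 62.5%, and Section 10.3.2.1 applies an MCID of -6 to those scores. That threshold only makes sense on a 0 to 100 scale.
- Section 10.3.2 needs a raw fraction inside the WPAI:GH work productivity loss formula. It writes out Q2 / (Q2 + Q4) there and does not reuse the absenteeism percentage defined just above.

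The SAP therefore keeps such quantities on the 0 to 100 scale, and in the WPAI:GH formula it writes the fraction out where one is required. Section 10.2.2.2 omits that step.

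**The case against.** The best defence is that a percentage is only a way of writing a proportion. On that reading 30.4375 days × 98% means 30.4375 × 0.98 = 29.83 days, which is right, and the error appears only if the percent sign is dropped and the bare number 98 is multiplied. The heading and both sentences use the word proportion, which usually means a fraction. The AE-QoL example can also be read as loose notation, since strictly 62.5% equals 0.625.

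This shows what was intended, and the intention is not in doubt. It does not repair the text. The displayed formula contains the number 100, so the quantity it defines is 98 and not 0.98, and the AE-QoL threshold and the compliance bands show that the SAP works with such numbers on the 0 to 100 scale.

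The points about consequence do stand:

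- Values in the thousands of days per month would very probably be caught in programming or table review, so an unnoticed false conclusion is unlikely.
- The quantity is not among the primary, secondary or exploratory endpoints of the protocol or SAP. It is a descriptive supplementary summary with no test attached.
- The count, the percentage and the period duration are correctly defined and reported alongside, so the right monthly value can be recovered.
- The slip is confined to this section. The per-month attack rates in Sections 10.2.1.1 and 10.2.1.3 are correctly scaled.

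These points limit the importance of the error. They do not make the derivation correct.

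**Conclusion.** The concern holds. Followed literally, the two consecutive definitions in SAP Section 10.2.2.2 give a monthly figure exactly 100 times too large for every subject with at least one attack-free day, up to 3,043.75 days in a 30.4375-day month. This rests only on the SAP's own formulas; the example subjects are illustrative and the factor does not depend on them.

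Whether any output would carry the error depends on whether the derivation is programmed literally, and the documents do not show that. The effect is confined to the monthly figure and its subgroup repeats. It is a scale error that should be corrected, with no bearing on the study's main conclusions.

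**What to change.** Replace the monthly rule in SAP Section 10.2.2.2 with:

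*Attack-free days per month = 30.4375 × (number of attack-free days / duration of the Efficacy evaluation period in days).*

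An equivalent wording is 30.4375 × percentage of attack-free days / 100. It would also help to call the first quantity the percentage of attack-free days throughout, so that one term does not stand for two scales.

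The cost is one line in the SAP and the matching line in the derivation specification, with no change to data collection or to any other analysis. If no further SAP version is planned, put the corrected formula in the derivation specification and record it in the clinical study report, where SAP Section 3 already says deviations will be described. A programming check that no subject's value exceeds 30.4375 would confirm that the correct scale was used.
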